13.3.4 Outcome computation conditions

1188 Outcomes will only be computed if at least 80% of the analysis window CGM measurements (after data
1189 treatment) are available

1190

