1145 As a early exploratory Study, the goal will be to complete up to 20 participants in the main study
1146 to provide data from a variety of individuals. This number was chosen out of feasibility and not
1147 from a formal power calculation. (The Pilot Study for this proposal will assess ease of system and
1148 will be completed in a minimum of 2-3 individuals prior to the beginning of the Main Study.) With
1149 N=20 and our randomized crossover design (allowing for paired comparison), we can hope to detect a
1150 minimum effect size of 0.66 at a power of 80%. Based of prior FCL study, the standard deviation of daytime
1151 TIR is approximately 12%, leading to a detectable difference in daytime TIR of 8%.

1152 **13.3 Outcome Measures**

1153 **13.3.1 Primary Efficacy Endpoint**

1154 The study design allows for multiple comparisons of blood glucose control during the study meals
1155 and exercise sessions, with for the primary comparison of interest being between the RocketAP
1156 with and without BPS. Our primary endpoint is CGM time-in-range 70-180 mg/dL for the daytime
1157 period 6 am – 12 am when on each treatment modality (BPS vs. no BPS).

1158 **13.3.2 Secondary Outcomes**

1159 Each admission is separated into windows of analysis:

- 1160 • The entirety of the admission (24h: 4pm to 4pm)
- 1161 • The 4 hours following each of the meals.
- 1162 • The overnight period (12 am to 6 am)

1163 For each of these periods we will compute the following outcomes:

- 1164 • Number of hypoglycemia events defined as at least two consecutive CGM values
1165 <70mg/dL or a hypoglycemia treatment (two events separated by less than 30 minutes are
1166 counted as one).
- 1167 • Percent CGM time <70 mg/dL
- 1168 • Percent CGM time between 80-140mg/dL
- 1169 • Percent CGM time between 70-180mg/dL
- 1170 • Percent CGM time >180 mg/dL
- 1171 • Percent CGM time >250 mg/dL
- 1172 • Units of insulin injected
- 1173 • Area under the curve when accounting for starting BG
- 1174 • Low Blood Glucose Index
- 1175 • High Blood Glucose Index
- 1176 • CGM coefficient of variation
- 1177 • Mean CGM

CLINICAL PROTOCOL

1179

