13.3.3 CGM data treatment

1180 • Saturated CGM values “High” and “Low” will be replaced by 401mg/dL and 39mg/dL
1181 respectively.

1182 • Any CGM gaps shorter than 1 hour will be interpolated
1183 • CGM data during recorded occlusion event will be removed from analysis as follow:
1184 any measurement less than 2h before or after the time of record will be removed.
1185 • CGM data following a pump/DiAs communication interruption >1h by less than 2h
1186 will be removed

1187

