13.4 Safety Analyses

1191 We will assess for the system’s functionality, including the ability of the system to run its code
1192 without error (delivering insulin safely, as planned), as well as its ability to avoid low BG <70
1193 mg/dL.

1194

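### The CGM deletion and 80% availability rules cover the hypoglycemia counts without exception, so observed lows, and in short windows treated lows too, can go uncounted

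*Combined protocol and SAP*

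**What the plan says.** Section 13.3.2 lists, for the whole 24 h session, the 4 h after each meal and the night from midnight to 6 am, a set of outcomes that mixes efficacy and safety. It includes percent time below 70 mg/dL, the Low Blood Glucose Index and "Number of hypoglycemia events defined as at least two consecutive CGM values" below 70 mg/dL or, as an alternative that needs no CGM reading, a hypoglycemia treatment.

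Section 13.3.3 then removes CGM data on two grounds. Around a recorded occlusion, "any measurement less than 2h before or after the time of record will be removed". The second ground is "CGM data following a pump/DiAs communication interruption >1h by less than 2h". Only gaps under 1 h are interpolated.

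Section 13.3.4 adds: "Outcomes will only be computed if at least 80% of the analysis window CGM measurements (after data" treatment) are available. Neither section separates safety outcomes from efficacy outcomes.

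Section 13.4 makes the safety aim that the system runs "without error (delivering insulin safely, as planned), as well as its ability to avoid low BG <70" mg/dL. It names no data set, window or exemption of its own. Section 11.2 leaves non-severe hypoglycemia out of adverse event recording unless it is associated with an adverse device effect.

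**The concern.** An availability threshold makes sense for a percentage, which is unreliable when much of its denominator is missing. An event that was seen or treated is different: it happened whether or not the surrounding CGM is complete. Here a threshold on CGM completeness decides whether a treatment is counted, although the event definition deliberately accepts treatments without CGM.

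The windows most easily lost are the ones that matter most for the question. Section 1.1 says the BPS might itself raise the risk of hypoglycemia and that it is silent from 23:00 to 6:00. Lows caused by a priming dose would therefore be looked for mainly after meals, and the 4 h post-meal window tolerates the least loss. Section 13.1.1 expects paired Wilcoxon tests for time below 70 mg/dL and event counts, so one void window removes that participant's pair from that comparison, out of about 20. The missing-data provision there is triggered by missing admissions, not by void windows.

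**Working it through.** **The plan's own figure.** The plan gives no figure for CGM loss. Its one calculation, in 13.2, is a "minimum effect size of 0.66 at a power of 80"% with 20 participants. A paired t-test with 19 degrees of freedom and two-sided alpha 0.05 (assumed; the plan states no alpha) has 79.9% power at 0.66, and 0.66 × 12% = 7.9%, given as 8%. It reproduces, and it does not depend on this point.

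**Inputs.** Window lengths W = 24, 6 and 4 h (13.3.2). Deleted block L = 4 h for an occlusion (2 h each side) and 2 h for an interruption (13.3.3). Required availability 80% (13.3.4). Interpolation cannot restore a block of 2 h or 4 h.

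**Step 1: loss allowed = 0.20 × W.** 24 h: 4.8 h. Overnight: 1.2 h = 72 min. Post-meal: 0.8 h = 48 min.

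**Step 2: availability after one fault = 1 − L/W, block wholly inside the window.**

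| Window | Interruption (2 h) | Occlusion (4 h) |
|---|---|---|
| 24 h | 22/24 = 91.7%, computed | 20/24 = 83.3%, computed |
| Overnight 6 h | 4/6 = 66.7%, void | 2/6 = 33.3%, void |
| Post-meal 4 h | 2/4 = 50%, void | 0/4 = 0%, void |

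The 24 h window fails only on combined losses: an occlusion plus a separate 1 h gap leaves 19/24 = 79.2%; an occlusion plus a separate interruption leaves 18/24 = 75.0%.

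**Step 3: fault times that void a short window.** The block need not lie wholly inside; the overlap only has to exceed the allowed loss. The span of such times is W + L − 2 × 0.20W.

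- Overnight, occlusion: 6 + 4 − 2.4 = 7.6 h (records from 23:12 to 06:48).
- Overnight, interruption: 6 + 2 − 2.4 = 5.6 h (ending from 23:12 to 04:48).
- Post-meal, occlusion: 4 + 4 − 1.6 = 6.4 h.
- Post-meal, interruption: 4 + 2 − 1.6 = 4.4 h.

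A short window that overlaps the block by no more than 48 or 72 min is still computed.

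**Step 4: what is lost where.** The deletions act on CGM, not on treatment records.

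- An untreated CGM low inside the block is lost from every window.
- A treated low is lost only where its window falls below 80%. After a single fault it is lost from a void post-meal or overnight count and kept in the 24 h count.
- A CGM low outside the block is lost only from a void window.

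**Step 5: direction.** These rules take events away and add none, so the total number of events reported can only be understated. (The one contrived exception is a single low lasting through a whole deleted block, which would be split in two.) Percent time below 70 mg/dL loses from numerator and denominator together. Take an assumed 1 h below 70 in 24 h, or 4.2%, and one 4 h deletion. If the low lies outside the block, the result is 1/20 = 5.0%; if inside, 0/20 = 0%. It can move either way.

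**The case against.** The deletions have a sound purpose. After loss of pump connectivity the pump reverts to pre-programmed basal delivery (1.5), and an occluded set does not deliver what the algorithm ordered. Leaving those hours out of a comparison of BPS states is defensible. This stands, and it is why the rules should stay for that comparison.

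Several stronger readings are tempting, and the documents do not support them.

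- A reader might infer that rescue treatments disappear altogether. They do not: treatment records are not deleted, and after a single fault the 24 h count keeps them.
- A reader might infer that nothing else records these lows. Severe hypoglycemia is reportable whatever the CGM availability (11.2.1) and goes to the Medical Monitor (8.2). A non-severe low to which the device may have contributed can be recorded through the adverse device effect route (11.1.4, 11.2). Section 13.6 tabulates malfunctions, CGM availability and closed-loop time. Other capture is limited, not absent. Section 11.8 itself leaves component disconnections and occlusions without ketosis out of device-issue reporting unless adverse event criteria are met.
- A reader might infer that 13.4 as written omits the fault periods. It does not invoke 13.3.3 or 13.3.4; it is silent on its data. Silence still leaves the 13.3.2 list as the only defined measures of glucose below 70 mg/dL.
- A reader might infer that hypoglycemia is biased low in both BPS states, or that the comparison is distorted. A void window is missing, not zero. Section 10.1.5 notes that a failing infusion set can cause hyperglycemia, so removing those hours could raise the remaining percent below 70. No document suggests that fault rates differ by BPS state.

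Materiality is also open. These are secondary outcomes of an exploratory, closely supervised study that expects little missing data.

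**Conclusion.** The point holds in a limited form. Following 13.3.3 and 13.3.4 as written discards CGM-observed lows in the deleted block from every window. It discards the whole hypoglycemia count, treatments included, from post-meal windows losing more than 48 min and overnight windows losing more than 72 min. One fault well inside a short window is enough; one fault alone never voids the 24 h window.

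The conclusion rests on reading outcomes in 13.3.4 as every item in 13.3.2, which is the plain reading because no exception is stated. The percentages in the table assume the block lies wholly inside the window, with the occlusion record at mid-window for the 4 h case. How many windows would be affected cannot be computed, since the documents give no occlusion or interruption rates. The defect is worth correcting because it bears on a named safety aim and the correction is cheap. It does not affect the primary analysis.

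**What to change.** Add to 13.3.3 and 13.3.4, with a cross-reference in 13.4:

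- For the safety assessment, hypoglycemia events, both CGM-detected and treated, are also counted on all CGM as recorded, before the 13.3.3 deletions, and on all treatment records, regardless of the 80% rule.
- The count is given by the BPS state in force, with hours observed as the denominator. Events in occlusion or interruption periods are flagged.
- Time below 70 mg/dL on the as-recorded CGM is reported as a supplementary figure, with hours observed.
- The current deletion and availability rules stay in force for the glycemic percentages and indices in the BPS comparison.

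The cost is a short addition to the text and one extra table from data already collected. The downside is that some counted events will come from periods when the algorithm was not in control of delivery; the flag lets a reader separate them.

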13.4 Safety Analyses

1191 We will assess for the system’s functionality, including the ability of the system to run its code
1192 without error (delivering insulin safely, as planned), as well as its ability to avoid low BG <70
1193 mg/dL.

1194

13.5 Baseline Descriptive Statistics

1195 Baseline demographic and clinical characteristics of the cohort of all randomized participants will
1196 be summarized in a table using summary statistics appropriate to the distribution of each variable.
1197 Descriptive statistics will be displayed overall and by treatment group.

1198 Will include:

1199 • Age
1200 • HbA1c
1201 • Gender
1202 • Race/ethnicity
1203 • CGM use before enrollment
1204 • AID use before enrollment
1205 • Diabetes duration
1206 • BMI
1207 • Total Daily Insulin

1208

13.6 Device Issues

1209 The following tabulations and analyses will be performed during time on the UVa AP systems to
1210 assess device issues:

1211 • Device malfunctions requiring study team contact and other reported device issues
1212 • % time CGM data available
1213 • % time with closed loop control

CLINICAL PROTOCOL

1214 **Chapter 14 Data Collection and Monitoring**

1215 **14.1 Case Report Forms and Device Data**

1216 The study data are collected through a combination of case report forms (electronic and paper) and
1217 electronic device data files obtained from the software and individual hardware components. These
1218 electronic device files and electronic CRFs are considered the primary source documentation.

1219 When data are directly collected in electronic case report forms, this will be considered the source
1220 data. Records will be maintained in accordance with ICH E6 and institutional regulatory
1221 requirements for the protection of confidentiality of participants.

1222 **14.2 Study Records Retention**

1223 Study documents should be retained for a minimum of 2 years after the last approval of a marketing
1224 application in an ICH region and until there are no pending or contemplated marketing applications
1225 in an ICH region or until at least 2 years have elapsed since the formal discontinuation of clinical
1226 development of the investigational product. These documents should be retained for a longer
1227 period, however, if required by local regulations. No records will be destroyed without the written
1228 consent of the sponsor, if applicable. It is the responsibility of the sponsor to inform the investigator
1229 when these documents no longer need to be retained.

1230 **14.3 Protocol Deviations**

1231 A protocol deviation is any noncompliance with the clinical trial protocol, Good Clinical Practices
1232 (GCP), or procedure requirements. The noncompliance may be either on the part of the participant,
1233 the investigator, or the study site staff. As a result of deviations, corrective actions may be
1234 developed by the site and implemented as appropriate. Major deviations will be reported to the
1235 IRB-HSR within 7 calendar days of when the study team becomes aware of the event.

CLINICAL PROTOCOL

1236 **Chapter 15 Ethics/Protection of Human Participants**

1237 **15.1 Ethics Standard**

1238 The investigator will ensure that this study is conducted in full conformity with Regulations for
1239 the Protection of Human Participants of Research codified in 45 CFR Part 46, 21 CFR Part 50, 21
1240 CFR Part 56, and/or the ICH E6.

1241 **15.2 Institutional Review Boards**

1242 The protocol, informed consent form(s), recruitment materials, and all participant materials will
1243 be submitted to the IRB for review and approval. Approval of both the protocol and the consent
1244 form must be obtained before any participant is enrolled. Any amendment to the protocol will
1245 require review and approval by the IRB before the changes are implemented to the study. All
1246 changes to the consent form will be IRB approved; a determination will be made regarding whether
1247 previously consented participants need to be re-consented.

1248 **15.3 Informed Consent Process**

1249 **15.3.1 Consent Procedures and Documentation**

1250 Informed consent is a process that is initiated prior to an individual's agreement to participate in
1251 the study and continues throughout the individual's study participation. Extensive discussion of
1252 risks and possible benefits of participation will be provided. Consent forms will be IRB approved
1253 and the participant will be asked to read and review the document. The investigator or their
1254 delegate will explain the research study to the participant and answer any questions that may arise.
1255 All participants will receive a verbal explanation in terms suited to their comprehension of the
1256 purposes, procedures, and potential risks of the study and of their rights as research participants.
1257 Participant will have the opportunity to carefully review the written consent form and ask questions
1258 prior to signing.

1259 The consenting process will involve discussing the study at length in a phone call/HIPAA
1260 compliant telecommunication method for consenting that is not face to face. The participant will
1261 sign the informed consent document prior to any procedures being done specifically for the study.
1262 The consent form may be signed electronically with the use of the Part 11 compliant version of
1263 DocuSign for both in-person and telecommunication screening visits. The study team will follow
1264 the FDA part 11 compliant process of verification of reviewing two forms of identification if
1265 signing electronically off site. A HIPAA compliant video conferencing tool will be utilized during
1266 the consenting process of the telecommunication screening visit to facilitate review of the
1267 participant's identification. A copy of the informed consent document will be given to the
1268 participant for their records. The rights and welfare of the participants will be protected by

CLINICAL PROTOCOL

1269 emphasizing to them that the quality of their medical care will not be adversely affected if they
1270 decline to participate in this study.

15.3.2 Participant and Data Confidentiality

1272 The study monitor, representatives of the IRB or device company supplying study product may
1273 inspect all documents and records required to be maintained by the investigator, including but not
1274 limited to, medical records (office, clinic, or hospital) for the participants in this study.

1275 The study participant's contact information will be securely stored at the clinical site for internal
1276 use during the study. At the end of the study, all records will continue to be kept in a secure
1277 location for as long a period as dictated by local IRB and Institutional regulations.

